Mild to moderate mucositis and conjunctivitis were associated with rash. The supportive-care measures included hydration, topical steroid preparations, oral corticosteroids, oral antihistamines, and oral antibiotics. Other common AEs included nausea, fatigue, vomiting, and diarrhea. These AEs were mild to moderate and in most cases were resolved by the standard supportive care and did not require therapy modifications. Hyperglycemia and hyperinsulinemia, both expected mechanism-based AEs, were observed in approximately 76% and 57% of patients, respectively, receiving MK-2206 on the QOD schedule. Episodes were generally mild, transient, and did not require therapeutic intervention. Importantly, administration of insulin may not counteract MK-2206-induced hyperglycemia due to mechanism-based insulin resistance. In this case, hydration and oral antihyperglycemic agents can be used as the supportive-care measures. Grade 3 hyperglycemia occurred in 1 patient who received 60 mg QOD and required treatment with PO antihyperglycemic medication. Grade 4 hyperglycemia was reported in one patient who received MK-2206 45 mg QOD in combination with erlotinib. In addition to supportive care measures, blood glucose management included administration of insulin and PO antihyperglycemic medication.

Grade 1/grade 2 prolongation of QTc-interval was observed in 14 out of 64 patients (21.9%) with available 12-lead ECG data. Prolongations ≥ 30 msec but < 60 msec occurred in 4 of these patients. Grade 3 QTc prolongation was reported in one patient who received 135 mg QW. Episodes of QTc interval prolongation were in general isolated with no apparent dependency on dose or exposure levels, and were not considered clinically significant by investigators and were not reported as adverse experiences. Eleven patients experienced sinus bradycardia (< 50 bpm) during Holter or ECG monitoring. These events were asymptomatic and were not clinically significant. While a causal relationship between these events and administration of MK-2206 is uncertain, similar side effects were seen preclinically in conscious dogs. Consequently, patients with a history or current evidence of heart disease should be excluded from enrollment on MK-2206 trials. Standard 12-lead ECG measurements should be performed at the protocol-specified time-points.

Developmental/Reproductive Toxicity

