3.2 Exclusion Criteria

- 3.2.1 Patients who received oral TKIs (sorafenib, sunitinib, or pazopanib) within 2 weeks prior to entering the study, radiotherapy, immunotherapy or chemotherapy within 4 weeks prior to entering the study, bevacizumab within 4 weeks prior to entering the study, or those who have not recovered from adverse events due to agents administered more than 4 weeks earlier (recovered to \leq Grade 1).
- 3.2.2 Patients may not be receiving any other investigational agents. Patients may not have received an mTOR inhibitor.
- 3.2.3 Patients with known brain metastases should be excluded from this clinical trial because of their poor prognosis and because they often develop progressive neurologic dysfunction that would confound the evaluation of neurologic and other adverse events.
- 3.2.4 History of allergic reactions attributed to compounds of similar chemical or biologic composition to MK-2206 or other agents used in the study.
- 3.2.5 Patients receiving any medications or substances that are strong inhibitors or inducers of CYP 450 3A4 are ineligible. Lists including medications and substances known or with the potential to interact with the CYP 450 3A4 isoenzymes are provided in [Appendix C](#).

- 3.2.6 Patient should have a Hemoglobin A1C value of < 8%. Preclinical studies demonstrated the potential of MK-2206 for induction of hyperglycemia in all preclinical species tested. Studies also demonstrate a risk of hyperglycemia, hyperlipidemia and hypertriglyceridemia associated with everolimus therapy. Patients with diabetes or in risk for hyperglycemia, hyperlipidemia and/or hypertriglyceridemia should not be excluded from trials with MK-2206 or everolimus, but the patient should be well controlled on oral agents (recent (i.e. within 3 months) HbA1C \leq 7.0) before the patient enters the trial.
- 3.2.7 Preclinical studies indicated transient changes in QTc interval during MK-2206 treatment. Prolongation of QTc interval is potentially a safety concern while on MK-2206 therapy. Cardiovascular: baseline QTcF > 450 msec (male) or QTcF > 470 msec (female) will exclude patients from entry on study. A list of medications that may cause QTc interval prolongation are listed in [Appendix D](#), and should be avoided by patients entering on trial.

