On-study evaluations will consist of the following study activities every four weeks +/- four days (Patients who are progression free after 1 year may have the following performed every 12 weeks +/- 7days):

- History and physical exam by physician, or mid-level provider at each scheduled visit.
- Vital signs (including weight) and ECOG performance status
- Serum chemistry including total protein, albumin, alkaline phosphatase, AST and/or ALT, calcium, LDH, total bilirubin, BUN, creatinine, phosphorus, uric acid, sodium, potassium, chloride, carbon dioxide, magnesium, and glucose at each scheduled visit (+/- 4 days). Hematology including CBC with differential and platelet counts and PT and PTT at each scheduled visit (+/- 4 days). T4, TSH, will be obtained at each scheduled visit (+/- 4 days). Amylase and lipase will be repeated at each scheduled visit as clinically indicated. Fasting lipid panel and glucose will be done every 4 weeks for the first 8 weeks and every 8 weeks thereafter. Cycle 1 Day 1 blood tests will not be done if screening labs were done in the previous 7 days.
- Serum glucose level monitoring for patients every 7 days +/- 2 days for patients on MK2206 during the first cycle of therapy. These measurements do not have to be performed at the study site, but data must be provided to the study team by the patient.
- Hemoglobin A1c levels need to be monitored at the beginning of each cycle for patients on MK2206 who require antihyperglycemic medication.
- Record concomitant medications at each scheduled visit.
- Monitor for adverse events. Treatment-related toxicity (acute and cumulative) will be performed every scheduled visit.
- On C1D1 only, patients randomized to MK-2206 will have an ECG within 4 hours of taking study drug.

Optional studies with patient consent:

- Blood will be drawn for a) plasma and serum analysis of cytokines and angiogenesis factors and b) circulating monocytic cells.

In addition to the above, the following will be performed every eight weeks +/- 7 days (Patients who are progression free after 1 year may have the following performed every 12 weeks +/- 7days):

- Repeat radiologic studies (CT, MRI, Chest x-ray and bone scan as indicated) to evaluate disease progression or response (in accordance with restaging of disease). Studies to confirm a complete response or document progressive disease will be performed as needed.
- 12-lead electrocardiogram (ECG)

End of Treatment

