7.1 Comprehensive Adverse Events and Potential Risks Lists (CAEPRs)

7.1.1 CAEPR for MK-2206

Comprehensive Adverse Events and Potential Risks list (CAEPR) for MK-2206 (NSC 749607)

The Comprehensive Adverse Events and Potential Risks list (CAEPR) provides a single list of reported and/or potential adverse events (AE) associated with an agent using a uniform presentation of events by body system. In addition to the comprehensive list, a subset, the Specific Protocol Exceptions to Expedited Reporting (SPEER), appears in a separate column and is identified with bold and italicized text. This subset of AEs (SPEER) is a list of events that are protocol specific exceptions to expedited reporting to NCI (except as noted below). Refer to the 'CTEP, NCI Guidelines: Adverse Event Reporting Requirements' http://ctep.cancer.gov/protocolDevelopment/electronic_applications/docs/aeguidelines.pdf for further clarification. Frequency is provided based on 245 patients. Below is the CAEPR for MK-2206.

NOTE: Report AEs on the SPEER **ONLY IF** they exceed the grade noted in parentheses next to the AE in the SPEER. If this CAEPR is part of a combination protocol using multiple investigational agents and has an AE listed on different SPEERs, use the lower of the grades to determine if expedited reporting is required.

Version 2.2, June 16, 2015¹

| Adverse Events with Possible Relationship to MK-2206 (CTCAE 4.0 Term) [n= 245] | | | Specific Protocol Exceptions to Expedited Reporting (SPEER) |
|--|--|------------------------|--|
| Likely (>20%) | Less Likely (<=20%) | Rare but Serious (<3%) | |
| BLOOD AND LYMPHATIC SYSTEM DISORDERS | | | |
| | Anemia | | |
| CARDIAC DISORDERS | | | |
| | Sinus bradycardia | | Sinus bradycardia (Gr 2) |
| GASTROINTESTINAL DISORDERS | | | |
| | Diarrhea | | Diarrhea (Gr 3) |
| | Mucositis oral | | Mucositis oral (Gr 3) |
| Nausea | | | Nausea (Gr 2) |
| | Vomiting | | Vomiting (Gr 3) |
| GENERAL DISORDERS AND ADMINISTRATION SITE CONDITIONS | | | |
| Fatigue | | | Fatigue (Gr 3) |
| | Fever | | Fever (Gr 2) |
| INVESTIGATIONS | | | |
| | Alanine aminotransferase increased | | |
| | Alkaline phosphatase increased | | |
| | Aspartate aminotransferase increased | | |
| | Creatinine increased | | |
| | Electrocardiogram QT corrected interval prolonged | | Electrocardiogram QT corrected interval prolonged (Gr 2) |
| | Hemoglobin increased | | |

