Additionally, toxicity will be monitored for the MK2206 arm. For the purpose of implementing this safety rule, toxicity will be defined as Grade 3 or greater toxicity that requires treatment discontinuation. The method of Thall, Simon and Estey (1995, 1996) will be used. Denoting the probability of toxicity by p , the trial will be stopped early if for the MK2206 arm, $\text{Prob}(p > 0.30 | \text{data}) > .93$. That is, if at any time during the trial, we determine that there is more than 93% chance that the toxicity rate for the MK2206 arm is greater than 30%, we will stop the trial. Assuming a $\text{beta}(0.6, .14)$ priori for p , the above decision criterion implies that we will stop the trial if $[\# \text{ patients with toxicities in the MK2206 arm}] / [\# \text{ patients evaluated in the MK2206 arm}] \geq 3/4, 4/5, 5/7, 6/9, 7/12, 8/14, 9/17, 10/20, 11/22, 12/25, 13/28, 14/30, 15/33, 16/36, 17/39, 18/42, 19/44, 20/47, 21/50, 22/53, 23/56, 24/59, 25/62, 26/65, 27/68$. The operating characteristics for this toxicity monitoring rule are illustrated in [Table 6](#).

Table 6. Operating Characteristics for Toxicity Monitoring Rule.

| True toxicity rate | Prob (stop the trial early) | Sample Size 25 th , 50 th and 75 th percentiles |
|--------------------|-----------------------------|---|
|--------------------|-----------------------------|---|

| | | |
|------|-------|------------|
| 0.10 | 0.005 | 70, 70, 70 |
| 0.20 | 0.047 | 70, 70, 70 |
| 0.30 | 0.288 | 41, 70, 70 |
| 0.40 | 0.784 | 8, 24, 61 |
| 0.50 | 0.990 | 4, 10, 19 |

This study will be monitored by the MDACC DSMB.

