13.4 Statistical Analysis Plan

The primary endpoint, progression-free survival (PFS), is defined as the time interval between date of treatment and date of disease progression, date of death or last follow-up date, whichever occurred first. The probability of PFS be estimated using the Kaplan-Meier method and will be compared between the two treatment arms using stratified log-rank test. Patients' safety data will be summarized by treatment arm, category, severity and relevance.

For secondary analyses, the Kaplan-Meier method will be used to estimate overall survival (OS) and time to failure (TTF), and stratified log-rank test will be used to compare between the two treatment arms. The OS is defined as the time interval between the date of treatment and the date of death or last follow-up, whichever occurred first. The TTF is defined as the time interval between the date of treatment and the date of disease progression, date of death, date of treatment discontinuation due to severe toxicity or last follow-up date, whichever occurred first. Overall response (OR) is defined as CR+PR and logistic regression model will be fit to assess the effect of treatment on the rate of OR.

Since the correlative studies being performed are by nature exploratory, and have not been

performed before in patients with RCC receiving mTOR inhibitors or AKT inhibitors, powering of these endpoints is not possible. Clinical benefit is defined as CR+PR+SD and again, we will fit logistic regression models to assess the effects of treatment, AKT activation, circulating cytokines and angiogenic factors, and karyotype on clinical benefit. The interaction effect between treatment and these exploratory factors will also be evaluated.

For virtual karyotyping, technique specific statistical analyses are outlined in [Appendix G](#).

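### Section 13.4 plans no summary of measured QTc or heart rate from the scheduled ECGs, so asymptomatic Grade 1/2 prolongation on MK-2206 may never reach the results

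*Combined protocol and SAP*

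**What the plan says.** Section 1.1 lists the safety of MK-2206 among the primary objectives. Section 3.2.7 states: "Prolongation of QTc interval is potentially a safety concern while on MK-2206 therapy". It sets entry limits of QTcF 450 msec for men and 470 msec for women. Appendix D lists QT-prolonging drugs, and the MK-2206 adverse-event list in 7.1.1 includes "Electrocardiogram QT corrected interval prolonged" as well as sinus bradycardia.

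Sections 5.2 and 10 schedule a 12-lead ECG in both arms at screening, every 8 weeks (12-weekly is allowed after one progression-free year) and at end of treatment. On Cycle 1 Day 1 only, "patients randomized to MK-2206 will have an ECG within 4 hours of taking study drug".

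The planned safety summary is one sentence in 13.4: "safety data will be summarized by treatment arm, category, severity and relevance". No section names a QTc or heart-rate variable, a change from baseline, a threshold or a between-arm comparison for the results.

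Section 2.2 describes the earlier experience. Grade 1/2 "prolongation of QTc-interval was observed in 14 out of 64 patients (21.9%) with available 12-lead ECG data", and in 4 of those patients the prolongation was at least 30 but less than 60 msec. It says that the episodes "were not considered clinically significant by investigators and were not reported as adverse experiences".

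**The concern.** Category, severity and relevance read as attributes of adverse events. If 13.4 is followed literally, a QTc reading enters the results only after an investigator has decided that it is an adverse event. Section 2.2 shows that, with this drug, that decision has gone the other way for measured prolongation.

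What is at stake is a primary objective. The trial could report little or no QTc effect on MK-2206 while its own ECGs show a low-grade one. It would also leave unused a set of randomized comparator ECGs from a drug that 2.3.3 describes as having no preclinical effect on QT.

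**Working it through.** **Inputs.** 14 of 64 patients with Grade 1/2 prolongation, 4 of them 30 to <60 msec (2.2). 70 patients planned on MK-2206 and 35 on everolimus, with median PFS assumed to be 8.2 and 4.9 months (13.2). ECGs every 8 weeks (5.2).

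**1. The plan's own figure.** 14/64 = 0.21875 = 21.9%, which reproduces. The exact (Clopper-Pearson) 95% CI runs from the 2.5th percentile of Beta(14, 51) to the 97.5th percentile of Beta(15, 50), that is 12.5% to 34.0%.

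**2. Carried over to this trial.** 70 × 0.21875 = 15.3. At the CI limits, 70 × 0.1251 = 8.8 and 70 × 0.3397 = 23.8. So about 15 patients, 9 to 24. The range reflects uncertainty in the earlier rate only.

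**3. The larger changes.** 4/64 = 6.25%, and 70 × 0.0625 = 4.4. So about 4 patients with an increase of 30 to <60 msec.

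**4. What an adverse-event table would show.** If a fraction r of the measured Grade 1/2 cases is recorded as adverse events, the table shows 70 × 0.21875 × r:
- r = 1: 15.3
- r = 0.5: 7.7
- r = 0: 0

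The documents do not give r for this trial. Section 2.2 describes r near 0 in earlier use.

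**5. Whether another provision catches Grade 1/2 findings.**
- The stopping rule in 13.1: "toxicity will be defined as Grade 3 or greater toxicity that requires treatment discontinuation". It pools all toxicities and covers MK-2206 only, so low-grade QTc is outside it.
- The dose-limiting toxicity definition in 5.4 takes in Grade 3 and 4 toxicity. The Grade 2 items it adds do not include QTc.
- The expedited-reporting exception for QTc in 7.1.1 is set at Grade 2, so events above Grade 2 are not exempt. Grade 1/2 events are.
- Section 7.4 requires every adverse event to be reported, but does not say when an ECG finding becomes one.

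Grade 3 or higher is therefore covered, and asymptomatic Grade 1/2 is not.

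**6. Which between-arm comparison the ECGs support.** With 30.44 days per month, median PFS is 4.9 × 30.44 = 149 days on everolimus and 8.2 × 30.44 = 250 days on MK-2206. Dividing by 56 days gives 2.7 and 4.5, so a patient treated to the planned median has about 2 eight-weekly ECGs on everolimus and 4 on MK-2206. A maximum rises with the number of readings. Comparing on-study maxima would thus tend to make MK-2206 look worse even with no drug effect, and restricting to visit types that both arms share does not equalise the counts. A comparison at one fixed visit avoids this.

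**The case against.** The strongest reply is that 13.4 speaks of safety data, which is not limited to adverse events, so a QTc table is unspecified rather than excluded. The plan is equally silent on its scheduled glucose, lipid and thyroid results. Both statements are correct. They make this an omission and not a contradiction, but an analyst can still follow 13.4 and produce no QTc result.

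Second, the earlier reporting pattern may not recur. The MK-2206 list in 7.1.1 (June 2015, 245 patients) places QTc prolongation in the category of up to 20%, not among the rare events. That list covers reported and potential events, so it does not prove that investigators now record these findings. It does make a table with no cases one end of a range rather than the forecast.

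Third, the earlier episodes were described as generally isolated and unrelated to dose or exposure, and only 4 of the 14 fell in the 30 to <60 msec band. This stands and is why both counts are given. It is also fair that the 8-weekly ECGs are not tied to the weekly dose (median Tmax was 4 to 10 hours) and that there are only 35 controls, so the summary would be descriptive.

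A reader might go further in four ways that the documents do not support:
- That the 13.4 summary is the whole of the safety evaluation. Section 13.1 adds a formal stopping rule and DSMB monitoring.
- That serious QTc harm could go unreported. Step 5 shows that Grade 3 or higher is covered, and 2.2 mentions a reported Grade 3 case.
- That ECG values are not collected, because the data schedule in Appendix K omits them. That schedule belongs to a generic multi-centre plan. It also omits concomitant drugs, which 5.3 requires the case report form to capture.
- That bradycardia combined with another heart-rate correction would hide prolongation. QTcF is the only correction named.

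Nor do the documents say why everolimus patients have ECGs.

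**Conclusion.** The concern holds for asymptomatic Grade 1/2 QTc prolongation. The plan names the risk and schedules the ECGs in both arms, but specifies no summary of the measured values. By the protocol's own account, reliance on adverse-event recording missed such findings before.

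The size is about 15 of 70 MK-2206 patients (9 to 24) with measured Grade 1/2 prolongation, and about 4 with an increase of 30 to <60 msec, against an adverse-event count anywhere from 0 up to the full number. This assumes that a rate from mixed doses and schedules carries over, and it treats the recorded fraction as unknown. The PFS design and the stopping rule are unaffected. The change is worth making because safety is a primary objective and the remedy is cheap.

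**What to change.** Add a paragraph to 13.4 specifying a descriptive summary from the ECGs already scheduled, using QTcF as in 3.2.7 and regardless of whether an adverse event was recorded:
- By arm, at each scheduled visit: QTcF, its change from baseline, and heart rate.
- By arm: numbers with an increase of at least 30 and at least 60 msec, numbers above 450 msec (men) or 470 msec (women), and numbers with heart rate below 50 bpm. These cut-points already appear in 2.2 and 3.2.7 and serve here only as reporting categories.
- Between arms: compare at one common fixed visit, for example change from baseline at the first 8-week ECG, stating how many patients in each arm have that ECG.
- On-study maxima: describe only, alongside the number of ECGs per patient.
- Cycle 1 Day 1 ECG: summarise for MK-2206 alone.

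The cost is entry of QT and heart rate for about 105 patients, where not already captured, and one table. It needs no new ECGs and changes no eligibility, dosing or stopping rule.

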1. OBJECTIVES

1.1 Primary Objectives

- 1.1.1 To assess progression free survival (PFS) of vascular endothelial growth factor (VEGF) therapy refractory renal cell carcinoma (RCC) patients who receive either MK-2206 or everolimus.
1. To assess safety of MK-2206 in patients with VEGF therapy refractory RCC

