In oncology studies with everolimus, severe pneumonitis suspected as drug-related has been reported as a serious adverse event on 13 occasions and additionally in the following associated preferred terms including acute respiratory distress syndrome (n=2), alveolitis (n=1) and allergic alveolitis (n=1), interstitial lung disease (n=10), lung infiltration (n=23), cryptogenic organizing pneumonia, lung consolidation, pulmonary alveolar hemorrhage, pulmonary toxicity and pulmonary fibrosis (n=1, each). One fatal case of drug-related pneumonitis was reported for a patient with metastatic infiltrating ductal carcinoma of the breast treated with 10 mg/day, which developed approximately two months after starting everolimus. Cytology for both the pleural and pericardial fluids was positive for malignancy. The death was considered possibly related to the underlying late stage tumor and study drug. Additionally, one patient treated with 10 mg/day died due to severe acute respiratory distress syndrome and septic shock. Thoracic CT scan demonstrated condensation in the majority of the left lower lobe and frosted glass appearance in the left upper lobe, lingula, and right lung.

Along with the cases of non-infectious pneumonitis, serious opportunistic infections have also been reported in cancer patients treated with everolimus:

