5.5 Duration of Therapy

In the absence of treatment delays due to adverse events, treatment may continue until one of the following criteria applies:

- Disease progression,
- Intercurrent illness that prevents further administration of treatment,
- Unacceptable adverse events(s),
- Patient decides to withdraw from the study, or
- General or specific changes in the patient's condition render the patient unacceptable for further treatment in the judgment of the investigator.
- Pregnancy

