13. STATISTICAL CONSIDERATIONS

13.1 Study Design/Endpoints

This is an open-label, multi-center, randomized phase II study. Patients will be randomized using 2:1 ratio to receive either MK2206 or everolimus. The primary endpoint of the study is progression-free survival (PFS), where an event is defined as either disease progression or death. The anticipated median PFS is 4.9 months and 8.2 months for the everolimus and MK2206 arms, respectively. The secondary endpoints include safety, overall survival (OS), overall response rate (ORR) and time to failure (TTF). For the primary endpoint, one interim futility analysis will be performed when a total of 38 events have occurred. The O'Brien-Fleming stopping boundaries using Lan-DeMets spending function will be used for early rejection of H1 (futility boundaries). At the interim look, if the nominal critical point (Z-scale) is less than 0.051, we will terminate trial, reject H1, and conclude that MK2206 has no significant effect on improving PFS. Assuming that the alternative hypothesis holds and trial is continued to completion without interim analysis, 105 patients with 75 events provide 81% power to reject null hypothesis. Since this trial has one interim analysis, 105 patients with 75 events provide 80% power to reject null hypothesis. Please see the detail information for power calculation in [section 13.2](#) sample size / power calculation.

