13.2 Sample Size/ Power Calculation

Assuming that the median progression-free survival (PFS) is 4.9 months and 8.2 months for the everolimus and MK2206 arm, respectively and patients will be randomized with 2:1 ratio into the MK2206 arm and the everolimus arm, then with a total of 75 events (i.e., disease progression or death), we will have an 80% power to detect such a 67% increase in median PFS using one-sided log-rank test and at a 0.10 significance level. The total number of patients to be enrolled will be 105, with 35 on the everolimus arm and 70 on the MK2206 arm. The above calculation also assumes an accrual rate of 4 patients per month, thus it will take 26.3 months to accrue all 105 patients. The maximum study duration will be around 29 months, which include patients' accrual period and a follow-up period. East5 software was used for the sample size/power calculation.

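### The by-arm safety summary makes no allowance for time on treatment, so if treatment durations differ, crude percentages for events that keep accruing would differ between arms even at equal hazards

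*Combined protocol and SAP*

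**What the plan says.** Section 13.4 gives safety one sentence: "safety data will be summarized by treatment arm, category, severity and relevance". It names no statistic and mentions neither person-time, time to first event, cumulative incidence nor a common observation window. No other section supplies one.

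Treatment is open-ended. Under Section 5.5, "treatment may continue until one of the following criteria applies", and the list includes progression, unacceptable adverse events, intercurrent illness and withdrawal. Appendix K (Section 5.0, Toxicity) has auditors confirm follow-up for toxicity for thirty days from the last protocol therapy, so the observation window moves with time on drug. Section 13.1 states: "The anticipated median PFS is 4.9 months and 8.2 months for the everolimus and MK2206 arms, respectively".

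Section 1.1 lists among the primary objectives: "To assess safety of MK-2206 in patients with VEGF therapy refractory RCC". Section 13.1 lists safety among the secondary endpoints.

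Two other items touch on toxicity, and neither fills the gap. The stopping rule in Section 13.1 is a raw per-patient proportion in the MK-2206 arm alone. Time to failure in Section 13.4 counts stopping for severe toxicity only within a composite with progression and death.

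**The concern.** The natural reading of a summary by arm, category and severity is a table of patients with at least one event, as counts and percentages. For an event that can begin at any time on drug, that percentage rises with the time observed. If one arm stays on treatment longer because its drug delays progression, its percentages go up for that reason alone. If its drug fails early, they go down.

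Everolimus is the only randomized reference for the tolerability of MK-2206. A reader of the planned table could not tell how much of a difference is toxicity and how much is time on drug. The direction of the distortion is not known in advance, which favours fixing the presentation before the data are seen.

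**Working it through.** **Design figures.** Sections 13.1 and 13.2 give medians of 4.9 and 8.2 months, 35 and 70 patients, 75 events, one-sided 0.10, accrual of 4 per month (105/4 = 26.25 months) and a maximum duration of about 29 months.

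**The plan's own figure.** The stated power is 80%, "using one-sided log-rank test and at a 0.10 significance level". The hazard ratio is 4.9/8.2 = 0.598, and |ln 0.598| = 0.515. By Schoenfeld's formula, 0.515 × √(75 × 2/3 × 1/3) − 1.282 = 2.102 − 1.282 = 0.820, which gives power 79.4%. Exponential PFS with uniform accrual gives 76.5 expected events at 29 months, consistent with 75. The design figures are coherent and can be used for exposure.

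**Time on treatment.** Take exponential PFS, with stopping only at progression. Then λ = ln 2/median, which is 0.1415 per month (everolimus) and 0.0845 per month (MK-2206).

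- Complete follow-up: mean 1/λ = 7.07 and 11.83 months, ratio 1.67.
- Entry uniform over 26.25 months, cut-off at 29 months: mean 5.81 and 8.06 months, ratio 1.39.

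**Percentage with at least one event.** Assume the same constant hazard h in both arms and an additional hazard d of stopping for other reasons. Put s = h + λ + d. Potential follow-up is uniform from 2.75 to 29 months, so

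P = (h/s) × [1 − (e^(−2.75s) − e^(−29s)) / (26.25 s)].

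Example with h = 0.05 and d = 0:

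- Everolimus: s = 0.1915, so 0.2612 × [1 − (0.5907 − 0.0039)/5.026] = 0.231.
- MK-2206: s = 0.1345, so 0.3717 × [1 − (0.6908 − 0.0202)/3.531] = 0.301.

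| h per month | Everolimus, d = 0 | MK-2206, d = 0 | Difference, d = 0 | Difference, d = 0.05 |
|---|---|---|---|---|
| 0.02 | 10.5% | 14.2% | 3.7 points | 2.4 points |
| 0.05 | 23.1% | 30.1% | 7.0 points | 4.7 points |
| 0.10 | 38.1% | 47.5% | 9.5 points | 6.7 points |

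**Upper bound.** With complete follow-up and stopping only at progression, P = h/(h + λ). This gives 12.4% against 19.1%, 26.1% against 37.2% and 41.4% against 54.2%, so differences of 6.7, 11.1 and 12.8 points.

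**Reversal.** If the median on MK-2206 were 3 months (assumed), the same formula gives 8.0%, 17.8% and 30.2% on MK-2206, a false deficit of 4.4, 8.3 and 11.2 points.

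**Early events.** If the event can occur only in month 1, the ratio of percentages is about 1.03. If only in months 1 to 3, it is about 1.07 to 1.08.

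The documents give no event rate per unit time and no drop-out rate, so h and d are assumptions shown as ranges. The 30-day tail is left out. Adding one month at h = 0.05 with complete follow-up, by P = 1 − [λ/(h + λ)]e^(−h), gives 29.7% against 40.2%, a gap of similar size.

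**The case against.** The strongest reply is that no between-arm safety inference is planned. The safety objective names MK-2206 only, the stopping rule covers that arm only, and Sections 11.1.1 and 13.5.1 define evaluability for toxicity only from first treatment with MK-2206. Section 13.4 compares PFS but only summarizes safety, and it does not say that percentages will be used. This stands: the plan is under-specified and descriptive, and no test or stopping decision turns on it. It does not remove the point, because a by-arm table will be read across the arms.

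The distortion is also smaller than sampling error in a trial of this size. With 35 and 70 patients, the standard error of the difference at the 29-month cut-off is √[p₁(1 − p₁)/35 + p₂(1 − p₂)/70], about 6.7, 9.0 and 10.1 points for the three hazards. Each false excess lies within one standard error. That limits what any single row can show, but the shift is systematic and pushes every accruing event in the same direction.

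Three stronger readings are tempting, and the documents do not support them:

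- A reader might infer that MK-2206 patients will be observed 67% longer. The medians are PFS under the alternative, not treatment durations. Section 5.5 lists other reasons to stop, and the study length reduces the ratio of mean times to about 1.39.
- A reader might infer that excess harm will appear on MK-2206. That happens only if its patients stay on drug longer, and only for events that keep accruing.
- A reader might take the fatal pneumonitis case in Section 2.3.5, "which developed approximately two months after starting everolimus", as showing the mechanism. A single onset, earlier than either design median, cannot show a hazard that persists. Section 7.1 also lists pneumonitis as possibly related to everolimus but, for MK-2206, among events with insufficient evidence of causation. It is a poor illustration of equal hazards.

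**Conclusion.** The gap is real and worth closing, but it does not threaten the primary analysis. At equal assumed hazards of 0.02 to 0.10 per month, the design's own PFS assumption produces a false excess on MK-2206 of about 4 to 9.5 points at the 29-month cut-off, or about 2 to 7 points with moderate stopping for other reasons. The 7 to 13 points under complete follow-up are an upper bound. These figures rest on exponential times, a constant event hazard, and a safety table cut at the stated maximum study duration. With equal time on drug the effect vanishes.

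**What to change.** In Section 13.4, keep the crude table and add beside it, by arm:

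1. Time on treatment.
2. For each category, all grades and Grade 3 or higher, the number of patients with a first event per 100 patient-months at risk, counted from first dose to 30 days after last dose.
3. For the same categories, cumulative incidence over a common window, such as the first two 4-week cycles.

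State that any between-arm safety statement is to be read alongside these, not from crude percentages alone.

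The cost is a few lines of text and one extra table. Appendix K (Section 3.3, Data Collection) already has onset dates, cycle start dates and last dose dates entered, so no new data are needed and nothing in patient management changes. The downside is that a per-time rate assumes a roughly constant hazard and can understate front-loaded toxicity in the arm treated longer. The common-window incidence is shown with it for that reason. That window in turn misses later events, which the rate captures.
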